1.1. Rationale for the Study

Nasolacrimal duct obstruction (NLDO) is a common ocular condition in the first year of life. Many cases will resolve spontaneously or with massage.¹⁻³ Many studies of primary treatment of NLDO have been reported. These case series have largely been retrospective, uncontrolled, and conducted in single centers.

In children with NLDO symptoms, Peterson and Robb found that 58 of 65 (89%) blocked ducts spontaneously resolved by 13 months of age.² Peterson and Robb did not report the age distribution for the cohort, but they do note that 67% percent of the spontaneous resolutions occurred before 6 months of age.² Nelson and colleagues reported that among 113 infants enrolled into a study between 1 month and 10 months of age (median age = 5 months), 107 (95%) had NLDO spontaneously resolved by 13 months of age.⁴ Ghuman and colleagues found spontaneous resolution in 128 (32%) of 402 eyes treated with massage and antibiotics by 13 months, however the ages at which the children had initiated medical management were not specified.⁵ Paul reported that among 55 children with infantile NLDO who were first examined at 3 months of age or younger, 51 of 55 (91%) had ducts that were open at 12 months.⁶ With regard to spontaneous resolution in children who still have NLDO symptoms by a certain age, the Paul report showed that among 37 eyes with NLDO symptoms at 6 months, 26 (70%) were clear without surgical intervention by 12 months of age and that among 23 eyes with NLDO symptoms at 9 months, 12 (52%) had cleared by 12 months.⁶ The substantial uncertainty regarding an estimate of spontaneous resolution is a primary reason for conducting the current study.

Probing is the most widely-used initial treatment for NLDO in infancy. Our group recently completed a prospective observational study which found a 78% (95% CI = 74% to 82%) success proportion of probing among children aged 6 to <12 months.⁷ This overall success proportion was similar to that reported by others,^{5, 8-10} better than the 69% reported by Katowitz and Welsh,⁸ though worse than the 92% reported by Robb.¹¹

Two differing approaches to nasolacrimal probing have been most often been used: (1) immediate office probing (early probing – generally soon after 6 months of age) and (2) medical management (episodic antibiotic eye drops with massage of the lacrimal sac) until 9-13 months of age followed by probing under general anesthesia or conscious sedation (deferred probing). The advantages of early probing are the avoidance of general anesthesia or conscious sedation, immediate resolution of symptoms, fewer physician visits, fewer antibiotic prescriptions, lesser cost per procedure, and possible prevention of fibrosis from inflammation in the nasolacrimal duct. The advantages of deferred probing include more subject comfort with the procedure and possible avoidance of a surgical procedure completely.

Both early and deferred probing approaches are usually successful for treatment of NLDO. Early probing done in the office setting with restraint and only topical anesthesia was successful in 92% of children in a retrospective review of a series of 2369 infants.¹² These authors found a decline in success proportions with this office-based approach after 9 months of age. Success proportions of 77% to 97% have been reported in children younger than 18 months with

124 conventional probing with anesthesia. In our previous prospective observational study of
125 probing, 84% of the probings performed in an office setting were done under one year of age and
126 64% of the probings performed in a surgical facility were done at one year of age or older.⁷ The
127 study found that the 239 eyes that underwent office probing procedures had a slightly lower
128 proportion with success (72% [95% CI = 66% to 78%]) compared with the 661 eyes that
129 underwent surgical facility probings (80% [95% CI = 77% to 84%]).⁷ Limiting the office
130 probing cohort to the 132 eyes from 105 subjects aged 6 to <10 months old, the proportion with
131 success was 75% (95% CI = 66% to 82%) and limiting the facility probing cohort to the 223
132 eyes from 183 subjects aged 12 to <16 months old, the proportion with success was 80% (95%
133 CI = 74% to 85%) (PEDIG, unpublished data). We speculated that the lower success with office
134 probings might be due to a less robust procedure (e.g., probe passed only once) being performed
135 in the office setting. However, because our study was not randomized and because the
136 investigators who performed office probings did so nearly exclusively, we could not eliminate
137 the possibility that subject selection bias and/or an investigator effect may be important factors
138 underlying the observed difference in success between the office and facility settings.

139
140 The optimal approach to the management of NLDO in the first year of life remains uncertain.
141 Our prospective observational data suggest a slightly reduced chance of success with immediate
142 office probing; however, immediate office probing may be more cost-effective even if the
143 proportion with success is lower. For a subject undergoing a single operation, immediate office
144 probing is less expensive than deferred probing in a facility because there is no fee for
145 anesthesia, the facility, or for medications prescribed during the pre-operative observation
146 period. Some portion of this lower cost would be offset however by the additional cost of a
147 second procedure if the initial office probing is not successful. Deferred facility probing is more
148 expensive per procedure; however, the overall costs are reduced by the number of children
149 whose NLDO spontaneously resolves while waiting to perform the procedure in a facility. This
150 has been widely discussed by clinicians and has been studied using clinical decision analysis.¹³
151 Using a hypothetical spontaneous resolution rate of 70%, Kassoff found that deferred facility
152 probing had a higher cost than immediate office probing.¹³ In a preliminary model developed
153 with the assistance of [name], we found that a hypothetical spontaneous resolution rate
154 of about 75% equalizes the costs between immediate office probing and deferred facility probing
155 and that a higher spontaneous resolution rate could cause the overall cost to shift in favor of
156 deferred facility probing being less costly (personal communication, 1/17/2008).

157 158 **1.2. Definitions**

159 **Nasolacrimal duct obstruction (NLDO)** is a blockage of the tear drainage system leading to
160 epiphora, increased tear film, and/or mucous discharge from the eyes in the absence of an upper
161 respiratory infection, ocular surface irritation or glaucoma.

- 162 • **Simple NLDO**— a single obstruction in the nasolacrimal duct which is easily passed during
163 the probing procedure
- 164 • **Complex NLDO**— a blockage or multiple blockages anywhere along the tear drainage
165 pathway that causes more difficulty than usual with probe passage, such as a blockage at the
166 valve of Hasner, a tight inferior turbinate blocking flow, canalicular problems, or multiple
167 obstructions in the NLD

168
169 **Congenital NLDO** is the onset of NLDO symptoms prior to 6 months of age.

170
171 **Epiphora** is tear overflow onto the periocular skin.
172
173 **Probing** is the passage of a metal nasolacrimal probe through one or both canaliculi and through
174 the nasolacrimal duct.
175
176 **Office probing** is a probing performed without sedation, general anesthesia, or anesthesiologist
177 attendance. Topical anesthesia is used along with restraint of the infant.
178
179 **Facility probing** is a probing performed under general anesthesia or conscious sedation in a
180 hospital outpatient surgery department or an ambulatory surgical center.
181
182 **Balloon catheter dilation** is the probing and dilation of the nasolacrimal duct with a hydrostatic
183 balloon catheter. LacriCATH from Quest Medical Inc., An Atrion Company, Allen, Texas.
184
185 **Nasolacrimal intubation** is the probing and placement of a temporary stent. The stent may be
186 mono- or bi-canalicular.
187
188 **Inferior turbinate infracture** is the nasal displacement of the inferior turbinate performed
189 surgically.

190 191 **1.3. Study Objectives**

192 The primary objective of the study is to determine the cost-effectiveness of treating NLDO using
193 immediate office probing compared with deferred probing in a facility setting. As part of the
194 primary objective, the study will determine the proportion of eyes experiencing spontaneous
195 resolution among subjects randomized to the deferred probing group.

196
197 Secondary objectives are:

- 198 • To determine the success proportion for eyes undergoing immediate office probing as an
199 initial procedure
- 200 • To determine the success proportion for eyes undergoing deferred facility probing as an
201 initial procedure

202
203 Additional objectives will be detailed in a separate analysis plan.
204

205 **1.4. Synopsis**

206 This study is designed to prospectively evaluate in subjects between 6 to <10 months of age the
207 cost-effectiveness of probing performed as soon as possible in the office compared with a period
208 of observation followed by a probing procedure in a surgical facility, if needed.
209

210 The primary treatment outcomes will be evaluated using the clinical signs assessment that our
211 research group has used in our previous studies of NLDO⁷: treatment success or failure,
212 determined with an assessment of the three clinical signs of nasolacrimal duct obstruction—
213 epiphora, increased tear lake, and mucous discharge. Treatment success for the primary outcome
214 at 18 months of age will be defined as the absence of these three clinical signs, regardless of
215 whether the subject underwent surgery or the NLDO spontaneously resolved without surgery.

216
217 The study is being coordinated by the Jaeb Center for Health Research in Tampa, Florida and is
218 being funded through a cooperative agreement from the National Eye Institute. The
219 organizational structure of the study group and study policies are detailed in the Pediatric Eye
220 Disease Investigator Group (PEDIG) Bylaws.

221
222 **Enrollment**

223 Children 6 to <10 months of age with epiphora, increased tear film, and/or mucous discharge
224 considered by the investigator to be due to NLDO will be enrolled into the study. It is estimated
225 that the study will enroll 220 children. The enrollment exam will include an assessment for
226 clinical signs of NLDO and an ocular exam.

227
228 **Randomization**

229 Each child will be randomized to one of the following two groups:

- 230 • Immediate office probing: probing to be performed in the office either the same day or within
231 two weeks (referred to as ‘immediate probing group’).
232 • Deferred facility probing: probing to be performed 26 to 30 weeks after enrollment if any of
233 the clinical signs persist at the 26-week visit (referred to as ‘deferred probing group’).

234
235 Randomization will be by subject so children undergoing surgery in both eyes will have both
236 eyes assigned to the same treatment group.

237
238 **Pre-surgery Treatment**

239 For the deferred probing group between randomization and the day of surgery:

- 240 • Lacrimal massage will be prescribed for use twice daily when discharge is present. Lacrimal
241 massage may also be prescribed for use at other times at investigator discretion.
242 • Antibiotic eye drops will be prescribed for use when discharge is purulent, with instructions
243 that they should be used until the purulent discharge is gone.

244
245 For the immediate probing group, whether to use lacrimal massage and/or antibiotic eye drops
246 during this time is at investigator discretion.

247
248 **Follow-up Phone Contact and Examination**

249 Subjects will have a phone call 12 weeks (± 2 weeks) after randomization and a visit 26 weeks
250 (± 2 weeks) after randomization. These contacts will be after surgery has occurred for the
251 immediate probing group and before surgery has occurred for the deferred probing group.

252
253 For the deferred probing group:

- 254 • Subjects whose NLDO has resolved at the 26-week visit will not undergo surgery, but will
255 return for the primary outcome exam at 18 months of age.
256 • Subjects whose NLDO has not resolved at the 26-week visit will undergo surgery within 4
257 weeks and will then return for the primary outcome exam at 18 months of age.

258
259 All subjects will have a primary outcome exam at 18 months of age (± 4 weeks). At the primary
260 outcome exam, a masked examiner will perform an assessment for the presence of epiphora,
261 increased tear film, or mucous discharge.

262
263 Additional visits are at investigator discretion.

264
265 **Surgery and Surgical Setting**

- 266 • Subjects in the immediate probing group will undergo probing performed in the office setting
- 267 within two weeks of randomization (could be same day).
- 268 • Subjects in the deferred probing group will undergo probing performed in an ambulatory
- 269 surgery center or hospital within four weeks after the 26-week visit if any clinical signs of
- 270 NLDO are present at the 26-week visit.

271
272 **Post-Surgical Treatment**

273 Antibiotic/steroid eye drops will be used 2-4 times daily for one week after surgery. For

274 recurrent NLDO occurring more than a week after surgery, an antibiotic will be prescribed.

275 Lacrimal massage may be prescribed at investigator discretion.

276

277 Reoperation prior to the primary outcome visit at 18 month of age visit is at investigator

278 discretion and can be probing in office, probing in a facility, nasolacrimal intubation, or balloon

279 catheter dilation. Reoperations should be timed such that the primary outcome visit at 18-month

280 of age is at least one month after surgery, or at least one month after tube removal for

[figure not shown]
281 nasolacrimal intubation procedures. Presence of one or more clinical signs of NLDO will be

282 verified prior to reoperation, either on the day of surgery or at a preoperative visit.

283
284

285
286
287
288

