4.1. Visit Schedule

Follow up consists of the following visits and scheduled contacts:

- A phone call 12 (± 2 weeks) weeks from randomization
- A visit 26 weeks (± 2 weeks) from randomization
- A masked primary outcome exam at 18 months of age (± 4 weeks)

Subjects should complete all follow-up exams regardless of whether their symptoms have improved and/or resolved, and regardless of whether they receive surgery.

Additional visits prior to the primary outcome exam are at investigator discretion.

4.2. 12-week Phone Call

Parents will receive a phone call from the clinical site 12 weeks (± 2 weeks) after randomization. The office probing group will have had surgery by the time of this call, whereas the deferred probing group will not have had surgery yet.

The main purpose of the call will be to keep in contact with the family; however, data will be collected on whether symptoms of NLDO are present.

4.3. 26-week Visit

Subjects will have a visit 26 weeks (± 2 weeks) from randomization. The office probing group will have had surgery by the time of this visit, whereas the deferred probing group will not have had surgery yet.

At the visit, an assessment for the clinical signs of NLDO (see section 2.4) will be performed. The assessment may be performed by any study-certified examiner at the site, including the investigator.

For subjects in the deferred probing group:

- If one or more clinical signs of NLDO are present, the subject will undergo probing in a facility (ambulatory surgery center or hospital) within 4 weeks and will return for the primary outcome visit at 18 months of age.
- If no clinical signs of NLDO are present, the subject's NLDO will be considered to have spontaneously resolved and the subject will not undergo surgery. The subject will return for the primary outcome visit at 18 months of age.
 - If a subject with both eyes enrolled in the study has clinical signs of NLDO in one eye but none in the other eye, the remaining affected eye will undergo surgery and the other eye will be treated as a having spontaneously resolved.
 - If signs return and are sufficiently persistent to warrant surgery, the subject may undergo probing (see section 5.1).

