634 The study may be discontinued by the Steering Committee (with approval of the Data and Safety
635 Monitoring Committee) prior to the preplanned completion of enrollment and follow-up for all
636 subjects.

637
638 **6.11. Contacts by the Jaeb Center for Health Research**

639 The Jaeb Center serves as the PEDIG Coordinating Center. The Jaeb Center will be provided
640 with the parent/guardian's contact information. The Jaeb Center staff may contact the
641 parent/guardian to maintain rapport or to facilitate visit scheduling. A subject newsletter, study
642 updates, and a study logo item and/or another type of small gift may be sent periodically.
643 Subjects (specifically their parents and guardians) will be provided with a summary of the study
644 results in a newsletter format after completion of the study by all subjects.

645
646 **6.12. Risk Assessment**

647 This protocol falls under DHHS 46.404 which is research not involving greater than minimal
648 risk.

649 **CHAPTER 7: SAMPLE SIZE ESTIMATION AND STATISTICAL ANALYSIS**

650
651 The estimation of sample size and statistical analysis plan are summarized below and will be
652 detailed in separate documents.

653
654 **7.1. Sample Size Estimation**

655 Given that the proportion of subjects with treatment success at 18 months of age is expected to
656 be similar for both treatment groups, particularly after reoperations are taken into account,
657 sample size is not being determined in the context of a treatment group comparison. Rather,
658 because the cost factor in the economic model to be used in the primary analysis is driven largely
659 by the proportion of deferred probing group subjects which have NLDO spontaneously resolve
660 without surgery, sample size is being determined within the context of the width of the
661 confidence interval on this proportion. Table 1 shows the 95% confidence interval on the
662 spontaneous resolution proportion given the specified spontaneous resolution proportions and the
663 specified numbers of subjects randomized.

664
665 **Table 1: Confidence Intervals for Proportion of Spontaneous Resolution in the Deferred**
666 **Probing Group**

Deferred Probing Group									
SR%	Number of Subjects Randomized to Deferred Probing Group ^a								
	100			150			200		
	N Probed	N SR ^b	95% CI on SR% ^c	N Probed	N SR ^b	95% CI on SR% ^c	N Probed	N SR ^b	95% CI on SR% ^c
25%	75	25	16 to 34%	112	38	18 to 32%	150	50	19 to 31%

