50%	50	50	40 to 60%	75	75	42 to 58%	100	100	43 to 57%
75%	25	75	66 to 84%	37	113	68 to 82%	50	150	69 to 81%
90%	10	90	84 to 96%	15	135	85 to 95%	20	180	86 to 94%

667
668 SR = spontaneous resolution

669
670 ^aThe total number randomized would be twice these numbers.

671
672 ^bN with SR = the expected number of subjects in the deferred probing group whose NLDO will
673 spontaneously resolve given the specified spontaneous resolution proportion and the specified
674 number of subjects randomized.

675
676 ^c95% CI on SR% = 95% confidence interval on the spontaneous resolution proportion given the
677 specified spontaneous resolution proportion and the specified number of subjects randomized.

678
679 With the proportion of subjects with spontaneous resolution determined with data from 100
680 subjects randomized to the deferred probing group, a point estimate of 50% would have a
681 confidence interval of 40% to 60%, while a point estimate of 75% would have a confidence

682 interval of 66% to 84% and a point estimate of 90% would have a confidence interval of 84% to
683 96%.

684

685 In order to have outcome data on 100 subjects randomized to the deferred probing group, and
686 accounting for 10% loss to follow up, the study plans to enroll 220 children total, half of which
687 will be randomized to each treatment group.

688

689 **7.2. Statistical Analysis**

690 **7.2.1. Primary Analysis**

691 The primary analysis will be a comparison of the cost effectiveness between treatment groups.

692 The analysis will be performed using an economic rollback model that takes into account for

693 each subject the cost of treatment and the treatment outcome at 18 months of age.

694

695 The primary estimate of cost will be based on the type, number, and setting of all procedures
696 performed between randomization and 18 months of age, and the drugs prescribed. These
697 utilization figures will be multiplied by the representative cost associated with each to determine
698 aggregate cost per subject. Representative costs will be determined by averaging the total
699 allowable cost for each procedure obtained from actual explanations of benefits to facilities and
700 providers as well as by obtaining data on such allowable costs for large insurers.

701

702 Effectiveness will be based on the primary outcome at 18 months of age. Treatment success will
703 be defined as the absence of any clinical signs (presence of epiphora, increased tear film, or

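### The spontaneous-resolution proportion that decides the primary analysis is per eye in section 1.3 but per subject in 7.1, Table 1 and 7.3, and 7.2.1 names no unit for the break-point comparison

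*Protocol*

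**What the plan says.** The protocol gives the spontaneous-resolution (SR) proportion two units.

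- **Eyes.** Section 1.3: as part of the "primary objective, the study will determine the proportion of eyes experiencing spontaneous" resolution among those randomized to deferred probing.
- **Subjects.** Section 7.1 sizes the trial on the precision of this proportion because cost is driven largely "by the proportion of deferred probing group subjects which have NLDO spontaneously resolve" without surgery. Footnote b of Table 1 counts subjects, and section 7.3 again speaks of deferred-group subjects.
- **Cost.** Section 7.2.1 builds an "aggregate cost per subject". The rationale in 1.1 says that deferred facility probing is more "expensive per procedure; however, the overall costs are reduced by the number of children" whose obstruction resolves during the wait.
- **Decision rule.** Section 7.2.1 compares the confidence interval for the observed SR proportion with a break point estimated at about 75%. It does not say whether the proportion is of eyes or of children.
- **Bilateral children.** Both eyes may be enrolled and share one assignment (section 1.4). Under section 4.3, if one eye has signs at 26 weeks and the other does not, "the remaining affected eye will undergo surgery and the other eye will be treated as a having spontaneously resolved". No sentence says how that child counts when the unit is the subject.

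**The concern.** This proportion is the quantity that decides the primary analysis. Its confidence limits, set against the break point, determine whether the trial concludes that office probing is less costly, that deferred probing is less costly, or that neither can be said.

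A bilateral child with one clear eye is one resolution out of two at eye level, yet still incurs a facility procedure. With cost added up per child, the break point is naturally a child-level quantity, and a proportion of eyes is not on the same scale. An analyst who follows 1.3 and one who follows 7.1 would both be following the protocol, would report different proportions, and could reach different conclusions from the same data.

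**Working it through.** **1. Which unit the design figures use.** Table 1 at SR 75% with 100 subjects: 0.75 ± z × √(0.75 × 0.25 / 100) = 0.75 ± z × 0.0433. With z = 1.96 this is 66.5% to 83.5%; with z = 2 it is 66.3% to 83.7%, which rounds to the printed 66% to 84%. With z = 2 all 12 cells of Table 1 are reproduced; with z = 1.96, 10 of 12 are, the other two differing only by rounding. So Table 1 is a plain binomial interval on subjects.

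**2. Inputs for comparing the units.**
- Bilateral share b: section 1.1 reports 132 eyes from 105 children aged 6 to <10 months who had office probing in the group's earlier study. (132 − 105)/105 = 27/105 = 0.257. This is a proxy; the protocol gives no share for this trial.
- Per-eye SR s: assumed equal in unilateral and bilateral children.
- Fellow-eye correlation ρ: not given, so taken from 0 to 1.

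**3. Child-level SR.** Both eyes of a bilateral child resolve with probability s² + ρs(1 − s). Therefore

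child-level SR = (1 − b)s + b[s² + ρs(1 − s)],

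and eye-level minus child-level SR = b × s(1 − s) × (1 − ρ). At s = 0.75 the gap is 0.257 × 0.1875 × (1 − ρ) = 0.0482 × (1 − ρ):

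| ρ | Eye-level SR | Child-level SR | Gap (points) |
|---|---|---|---|
| 0 | 75% | 70.2% | 4.8 |
| 0.5 | 75% | 72.6% | 2.4 |
| 0.7 | 75% | 73.6% | 1.4 |
| 1 | 75% | 75.0% | 0 |

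**4. When the direction reverses.** An eye-level proportion weights bilateral children twice. If their per-eye SR is q and unilateral SR is u, eye-level SR is [(1 − b)u + 2bq]/(1 + b), and child-level SR is (1 − b)u + b[q² + ρq(1 − q)]. With u = 75%, the eye-level figure falls below the child-level one when q is below about 54% at ρ = 0.5, or about 67% at ρ = 0.8. Example at ρ = 0.7 and q = 60%: eye level (0.557 + 0.308)/1.257 = 68.9%; child level 0.557 + 0.257 × 0.528 = 69.3%.

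**5. Can the unit change the conclusion?** Take 100 children, hence about 126 eyes, equal SR and ρ = 0.5. To isolate the unit, give the eye-level estimate an interval that allows for clustering, with design effect 1 + 2bρ/(1 + b) = 1 + 0.257/1.257 = 1.204.

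- *Eye-level SR 83%.* Eyes: 0.83 − 1.96 × √(0.1411 × 1.204/126) = 0.83 − 0.072, lower limit 75.8%, above 75%, so deferred probing is less costly. Children: SR = 0.743 × 0.83 + 0.257 × (0.6889 + 0.0706) = 81.2%; lower limit 0.812 − 1.96 × √(0.812 × 0.188/100) = 73.5%, so no conclusion.
- *Eye-level SR 68%.* Eyes: upper limit 0.68 + 1.96 × √(0.2176 × 1.204/126) = 76.9%, so no conclusion. Children: SR = 0.743 × 0.68 + 0.257 × (0.4624 + 0.1088) = 65.2%; upper limit 0.652 + 1.96 × √(0.652 × 0.348/100) = 74.5%, below 75%, so office probing is less costly.

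In both cases only the unit differs.

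**The case against.** The best reply is that Chapter 7 already reads as a subject-level analysis. Section 7.2.1 follows 7.1, which introduces the proportion as one of subjects precisely because it drives cost, and 7.3 repeats this. A reader might infer from 1.3 that the plan will test an eye-level proportion against the break point. The protocol does not say so; what stands is a conflict between sections and a decision rule silent on the unit. But 1.3 is where the primary objective is set out, so the conflict cannot be dismissed as loose wording elsewhere. A separate analysis plan cannot resolve it quietly either, since either choice would contradict one section of the protocol.

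A reader might also infer that the planned interval is too narrow because fellow eyes would be treated as independent. The documents do not support that. The protocol specifies no eye-level interval, and handling of fellow-eye correlation may properly sit in the separate analysis plan.

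Nor is it established that an eye-level figure always favours deferred probing. That needs bilateral eyes to resolve about as often as unilateral ones and a correlation below 1.

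Finally, the gap is modest beside a planned interval of about ±9 points and a break point that is itself preliminary. That is fair, and it limits the importance of the point to results near the decision limits.

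**Conclusion.** The protocol contradicts itself on the unit of the proportion that decides its primary analysis, and the rule in 7.2.1 does not settle it. The difference is 0 to about 5 points at an eye-level SR of 75%. That rests on a bilateral share borrowed from an earlier cohort, equal per-eye resolution in unilateral and bilateral children, and an unknown fellow-eye correlation. The sign can change if bilateral eyes resolve much less often. The effect is small, but enough to move the conclusion between a verdict and no verdict near the break point. That the break point is a child-level quantity is inferred from the per-subject cost text; the protocol does not state the unit of its preliminary model. The sample size is not in question, since it already rests on subjects.

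**What to change.** - In sections 1.3 and 7.2.1, name the subject as the unit of the SR proportion that is compared with the break point.
- State the rule for bilateral children: a child counts as resolved only if every study eye meets the section 4.3 criterion, that is, no clinical signs at the 26-week visit and no surgery before it. Absence of surgery alone should not be the definition, because section 6.2 describes children who have not met the criterion for resolution but forgo surgery.
- State that the break point is derived per child, so that both sides of the comparison are on one scale.
- Keep the proportion of eyes with resolution as a secondary estimate, with an interval that accounts for clustering by child (for example, GEE or a cluster-robust variance).

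The cost is a few sentences in 1.3 and 7.2.1, and a check that the economic model uses the same unit. The 220 children, Table 1 and the data collected are unchanged.
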